### **3.1.2 Additional Cohort 2 Eligibility Criteria**

Patients enrolling to Cohort 2 must meet at least one of the following criteria:

1. ECOG performance status of 2 (see Appendix A)
2. Reduced organ function defined as:
  - a. Creatinine clearance 30-75 mL/min; or
  - b. Bilirubin 1.5-2  $\times$  IULN; or
  - c. ALT and AST 2.5-5  $\times$  IULN

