### **3.1.1 Additional Cohort 1 Eligibility Criteria**

Patients enrolling to Cohort 1 must meet all of the following criteria:

1. ECOG performance status 0-1 (see Appendix A).
2. Adequate organ function defined as:
  - a. Serum creatinine  $\leq 1.5 \times$  IULN and creatinine clearance  $\geq 75$  mL/min
  - b. Bilirubin  $\leq 1.5 \times$  IULN
  - c. ALT and AST  $\leq 2.5 \times$  IULN

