#### **14.4 Study Population**

Twenty-four eligible patients with p16INK4a negative/HPV-unrelated OPSCC, larynx SCC, hypopharynx SCC, and oral cavity SCC will be enrolled into the trial to receive 2 months of neoadjuvant palbociclib monotherapy at Step One, 6-7 weeks CRT (either cisplatin or cetuximab) at Step Two, and 6 months of adjuvant palbociclib at Step Three. The sampling method is non-random. Patients with excellent performance status and adequate vital organ function at enrollment will be assigned to the cisplatin cohort. Patients with reduced performance status and/or vital organ function will be assigned to the cetuximab cohort.

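### Cohort 2 entry on any one listed item leaves the stated limits on the other measures unenforced, and the two cohort definitions leave some patients in neither cohort

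*Combined protocol and SAP*

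**What the plan says.** Section 3.1.1 is conjunctive: "Patients enrolling to Cohort 1 must meet all of the following criteria". These are ECOG 0-1, serum creatinine at most 1.5× IULN together with CrCl of at least 75 mL/min, bilirubin at most 1.5× IULN, and ALT and AST at most 2.5× IULN.

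Section 3.1.2 is disjunctive: "Patients enrolling to Cohort 2 must meet at least one of the following criteria". The first item is ECOG 2. The second is reduced organ function, made up of three alternatives: "Creatinine clearance 30-75 mL/min; or", then "Bilirubin 1.5-2" × IULN, also followed by 'or', then "ALT and AST 2.5-5" × IULN. Serum creatinine does not appear in this list.

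Section 14.4 describes the split without figures: "Patients with reduced performance status and/or vital organ function will be assigned to the cetuximab cohort". Section 14.1 likewise assigns cohorts by performance status and organ function at enrolment.

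The criteria common to both cohorts do not cover these measures. Section 3.1 limits marrow function and QTc. Section 3.2 excludes uncontrolled intercurrent illness, cirrhosis, and renal or liver transplant. Neither gives an ECOG ceiling, a CrCl floor, or a bilirubin or transaminase ceiling.

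**The concern.** The Cohort 2 items are closed ranges, which look like the outer edge of the population the sponsor was willing to enrol. An 'at least one' rule does not make them work that way: once one item is met, the others are not tested. The two lists are also meant to divide the trial population, yet a conjunctive rule and a disjunctive rule divide it cleanly only if each item in one is the complement of its counterpart in the other. The transaminase and creatinine items are not.

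Two things are at stake.

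- **Safety in the frailer cohort.** Section 5.2.1 gives both cohorts the same starting dose of palbociclib, and Section 6.1 adjusts it only for toxicity on treatment. In Step One, Section 5.3.2 and the Section 10.1 calendar schedule CBC repeatedly but the metabolic panel only at baseline. Eligibility is thus the main documented check on renal and hepatic function for that step. Parts of the pharmacology section were not available to me, so this rests on the text I could read.
- **Cohort assignment.** Cohort decides whether cisplatin or cetuximab is given in Step Two, and Section 14.6.2 reports relapse, metastasis, PFS and OS by cohort. Every intended patient should belong to exactly one.

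**Working it through.** The plan gives no figure to reproduce here, so the check is one of logic.

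**Rules as written** (bilirubin, ALT, AST and serum creatinine in multiples of IULN; CrCl in mL/min):

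- Cohort 1 = ECOG 0-1 AND creatinine ≤ 1.5 AND CrCl ≥ 75 AND bilirubin ≤ 1.5 AND ALT ≤ 2.5 AND AST ≤ 2.5
- Cohort 2 = ECOG 2 OR CrCl 30-75 OR bilirubin 1.5-2 OR (ALT 2.5-5 AND AST 2.5-5)

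The literal 'and' in the last item is the natural reading, because the same word in Section 3.1.1 plainly requires both enzymes. The alternative, 'ALT or AST', was checked as well.

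**Profiles put through both rules.** Measures not named are normal.

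| Profile | Cohort 1 | Cohort 2, literal | Cohort 2, 'ALT or AST' |
|---|---|---|---|
| ECOG 2, CrCl 15 | no | yes | yes |
| ECOG 2, bilirubin 4× | no | yes | yes |
| ECOG 3 or 4, CrCl 50 | no | yes | yes |
| ECOG 0, CrCl 50, bilirubin 6×, ALT and AST 10× | no | yes | yes |
| ECOG 1, CrCl 20 | no | no | no |
| ECOG 1, ALT 3×, AST 1.5× (or the reverse) | no | no | yes |
| ECOG 1, ALT 6×, AST 3× | no | no | yes |
| ECOG 1, creatinine 1.6×, CrCl 80 | no | no | no |
| ECOG 1, CrCl exactly 75 | yes | yes | yes |
| ECOG 1, bilirubin exactly 1.5× | yes | yes | yes |
| ECOG 1, ALT and AST both exactly 2.5× | yes | yes | yes |

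**What follows.**

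1. *Outer limits.* Rows 1 to 4 are admitted although at least one measure lies beyond its listed limit. Row 5 marks the extent of this: with CrCl as the only abnormality, the floor of 30 does exclude the patient. A limit lapses only when the patient qualifies on something else.
2. *Transaminase gap.* Row 6 fails Cohort 1 on one enzyme and fails Cohort 2 because the other enzyme is too low. Reading the item as 'or' closes this gap, but row 7 shows that the change by itself would admit ALT 6× on the strength of AST 3×. The two repairs have to be made together.
3. *Creatinine gap.* Row 8 fails only the Cohort 1 serum creatinine condition. With CrCl above 75 it meets no Cohort 2 item on either reading. Section 14.4, read on its own, could send this patient or the one in row 6 to the cetuximab cohort as having reduced organ function. Section 3.1.2 does not.
4. *Overlap.* The last three rows satisfy both definitions, but only at single exact values.

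**The case against.** The best reply is that the ranges are evidently meant as bounds. Nobody writes CrCl 30-75 or bilirubin 1.5-2× without intending the far end to matter. ECOG 4, or bilirubin 6×, is a constructed extreme. The exclusions in Section 3.2 would remove some such patients. Section 4.1 also requires a signed eligibility checklist with source documents, and that checklist, which is not in the documents, may apply the limits.

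The point about intent is probably right, and nothing in the plan suggests that such patients are sought. It does not answer the concern. The exclusions carry no numeric limit on these measures, and a checklist that follows Section 3.1.2 has no ground to refuse a patient who meets one item and lies far outside another. If caps were intended, the amendment only writes them down.

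Other objections stand and limit the point:

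- A reader might infer that the listed limits have no force at all. They do: each binds a patient who qualifies on that measure alone.
- A reader might infer a loss of power, or that patients beyond the limits would miss the end-of-Step-One CT. The documents support neither. They do not say how many such patients would enrol or how they would fare, and losing one patient of 24 costs the same power whatever the reason.
- A reader might infer that the overlap threatens the by-cohort endpoints. It arises only at exact shared values, and Section 14.6 treats all analyses as exploratory and descriptive.

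**Conclusion.** The point holds as a defect in the stated eligibility rule. A patient who enters Cohort 2 on one measure is not held to the listed limit on any other. Two kinds of patient fall between the cohorts: those with a single transaminase above 2.5× IULN, and those with serum creatinine above 1.5× IULN and CrCl above 75 mL/min, all else being normal in each case. The first gap depends on reading 'ALT and AST' literally; the second does not. The overlap at exact boundaries is real but minor.

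The number of patients affected cannot be derived from the documents. The pooled primary test against 17% is not changed numerically. The case for acting rests on safety in the cohort meant for frailer patients and on unambiguous assignment. It assumes that no limit on these measures sits in the text I could not read or in the eligibility checklist.

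**What to change.** Reconcile Sections 3.1.1, 3.1.2 and 14.4 in one amendment.

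1. The sponsor should confirm whether the Cohort 2 ranges are meant as caps on every Cohort 2 patient. If so, change the opening condition of 3.1.2 to *at least one of the following, and no measure beyond the outer limits listed here*, using the figures already in the plan.
2. Change the transaminase item to *ALT and/or AST*, together with step 1 so that neither enzyme may exceed the listed limit.
3. Make the shared boundaries non-overlapping for CrCl, bilirubin and ALT/AST, with a strict inequality on one side of each.
4. State which cohort, if either, takes patients who fail only the Cohort 1 serum creatinine condition.
5. Have Section 14.4 refer to 3.1.1 and 3.1.2 instead of restating the split loosely, and bring the eligibility checklist into line.

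No new clinical threshold is needed; which limits are right is for the sponsor. The cost is amendment wording and a checklist revision. The downside is that a rare patient outside the listed limits becomes ineligible.

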## **3.2 Exclusion Criteria**

1. Diagnosis of cutaneous, paranasal sinus, salivary, or nasopharynx SCC, or diagnosis of neck nodes with unknown primary.
2. Diagnosis of P16/HPV-ISH positive OPSCC.
3. Presence of distant metastatic disease.
4. Prior systemic therapy for current diagnosis of HNSCC.
5. A history of other malignancy  $\leq 2$  years previous with the exception of basal cell or squamous cell carcinoma of the skin which were treated with local resection only or low risk/curatively treated prostate, thyroid, and cervical cancers.
6. Currently receiving any other investigational agents.
7. Treated within the last 7 days prior to Day 1 of protocol therapy with:

- a. Food or drugs that are known to be STRONG CYP3A4 inhibitors (e.g. grapefruit juice, verapamil, ketoconazole, miconazole, itraconazole, erythromycin, clarithromycin, telithromycin, indinavir, ritonavir, nelfinavir, atazanavir, amprenavir, nefazodone, diltiazem, and delavirdine) or inducers (e.g. glucocorticoids, progesterone, rifampin, phenobarbital, St. John's wort) [moderate CYP3A4 inhibitors/inducers are okay]
  - b. Drugs that are known to prolong the QT interval
  - c. Drugs that are proton pump inhibitors
8. A history of allergic reactions attributed to compounds of similar chemical or biologic composition to palbociclib, cisplatin (for Cohort 1), or cetuximab (for Cohort 2).
9. Uncontrolled intercurrent illness including, but not limited to, ongoing or active infection, symptomatic congestive heart failure, unstable angina pectoris, cardiac arrhythmia, or uncontrolled electrolyte disorders that can compound the effects of a QTc-prolonging drug (e.g. hypocalcemia, hypokalemia, hypomagnesemia).
10. History of cirrhosis.
11. History of renal or liver transplant.
12. Pregnant and/or breastfeeding. Women of childbearing potential must have a negative serum pregnancy test within 28 days of study entry. Female patients must be surgically sterile or be postmenopausal, or must agree to use effective contraception during the period of the trial and for at least 90 days after completion of treatment.
13. Known HIV-positivity and on combination antiretroviral therapy because of the potential for pharmacokinetic interactions with palbociclib. In addition, these patients are at increased risk of lethal infections when treated with marrow-suppressive therapy.

### **3.3 Inclusion of Women and Minorities**

Both men and women and members of all races and ethnic groups are eligible for this trial.

## **4.0 REGISTRATION PROCEDURES**

**Patients must not start any protocol intervention prior to registration through the Siteman Cancer Center.**

The following steps must be taken before registering patients to this study:

1. Confirmation of patient eligibility
2. Registration of patient in the Siteman Cancer Center database
3. Assignment of unique patient number (UPN)

#### **4.1 Confirmation of Patient Eligibility**

Confirm patient eligibility by collecting the information listed below:

1. Registering MD's name
2. Patient's race, sex, and DOB
3. Three letters (or two letters and a dash) for the patient's initials
4. Copy of signed consent form
5. Completed eligibility checklist, signed and dated by a member of the study team
6. Copy of appropriate source documentation confirming patient eligibility

#### **4.2 Patient Registration in the Siteman Cancer Center OnCore Database**

All patients must be registered through the Siteman Cancer Center OnCore database.

#### **4.3 Assignment of UPN**

Each patient will be identified with a unique patient number (UPN) for this study. All data will be recorded with this identification number on the appropriate CRFs.

### **5.0 TREATMENT PLAN**

“The three step” trial is a two cohort, non-randomized phase II trial in which palbociclib will be integrated into the standard CRT regimen with either cisplatin (cohort 1) or cetuximab (cohort 2). Patients with stage III-IV (non-metastatic) p16INK4a negative, HPV-unrelated HNSCC will be enrolled, to enrich the fraction of patients most likely to benefit from a CDK4/6 inhibitor.

During step one, patients in both cohorts will be treated with neoadjuvant palbociclib monotherapy (125 mg/day, Days 1-21 of a 28-day cycle for two cycles). A CT scan of the neck to assess tumor response and a tumor biopsy for pharmacodynamics assessment will be performed before and after palbociclib (CT scan – Cycle 2 post-treatment Day 21 through Day 25; Tumor biopsy Cycle 2 Day 21). Data will be pooled from the two cohorts to address the primary aim. The primary aim of the trial is to determine the tumor response rate (using RECIST 1.1) of newly diagnosed p16INK4a negative, HPV-unrelated HNSCC to palbociclib monotherapy given over two cycles, and to explore potential pharmacodynamic determinants of tumor response to palbociclib monotherapy using data derived from genomic, RNA, and protein expression methods performed on pre- and post-treatment tumor tissue.

During step two (CRT), Cohort 1 patients will be treated with cisplatin 100 mg/m^2 given on Days 1 and 22 with RT. Cohort 2 patients will be treated with cetuximab given one week before RT and then weekly during RT. Cohorts 1 and 2 will receive accelerated IMRT 70 Gy to be administered over 6 weeks in once daily fractions Monday through Friday, with one additional fraction of RT administered on (preferably) Fridays. The two fractions administered on one day will be at least 6 hours apart. Palbociclib, an oral agent, will not be given during step two due to the severe difficulty with swallowing that occurs in all patients treated with CRT and due to the lack of feasibility

studies for this combination therapy. To assess overall tumor response (stratified by cohort), a CT scan of the neck will be performed 8-10 weeks following completion of CRT, and FDG-PET/CT will be performed 14-18 weeks following completion of CRT.

During step three, patients in both cohorts will be treated with adjuvant palbociclib 125 mg/day, days 1-21 of each 28-day cycle for six cycles. Adjuvant palbociclib will begin 16 to 22 weeks following completion of CRT.

## **5.1 Premedication Administration**

No premedications are required for palbociclib.

Recommended premedications for cisplatin are: palonosetron 0.25 mg IVPB, dexamethasone 20 mg IVPB, and fosaprepitant 150 mg IVPB. In addition, hydration consisting of 1L IVF NS (also recommended: 10 meq KCl/L + 8 meq MgSO4/L) over 60 minutes before and after cisplatin on the day of dosing is recommended, and 2L IVF NS over 60 minutes on the 2 days following cisplatin dosing is recommended.

Recommended premedications for cetuximab are: diphenhydramine hydrochloride 50 mg (or an equivalent antihistamine) IVPB given at least 30 minutes prior to cetuximab, 1L IVF NS, hydrocortisone 100 mg IVPB, and/or albuterol inhalation (by nebulizer or inhaler) according to standard of care procedures.

## **5.2 Agent Administration**

### **5.2.1 Steps One and Three (Both Cohorts)**

Neoadjuvant palbociclib monotherapy will be given at a dose of 125 mg/day on Days 1-21 of two 28-day cycles during Step One. Adjuvant palbociclib monotherapy will be given at a dose of 125 mg/day on Days 1-21 of six 28-day cycles during Step Three.

Palbociclib is an oral drug available as capsules (or as liquid suspension). **The capsules should be taken with food.** Patients will be required to keep a drug diary (see Appendix B).

If a patient misses a day's dose entirely, s/he must be instructed not to make it up the next day but to just take his/her regular dose the following day. If a patient vomits any time after taking a dose, s/he must be instructed not to make it up but to resume subsequent dosing the next day as prescribed. If a patient inadvertently takes an extra dose during a day, s/he must be instructed to not take the next day's dose.

For patients who cannot swallow the palbociclib capsules, an oral solution will be available. Patients who begin the study receiving the oral solution will remain on the oral solution for the duration of their time on treatment in the study. Patients,

who begin the study receiving capsules but develop difficulty swallowing the capsules and did not have disease progression will be allowed to switch to the palbociclib oral solution. These patients will then remain on the oral solution for the duration of their time on treatment in the study. Each clinical site will be provided the oral solution Investigational Product Manual (IPM) containing the dosage and administration instructions (DAI) for preparation of the palbociclib oral solution. **Patients can take palbociclib oral solution with or without food.**

### **5.2.2 Step Two, Cohort 1**

Cohort 1 patients will receive accelerated IMRT for a total dose of 70 Gy. It will be given over 6 weeks in once daily fractions Monday through Friday, with one additional fraction given on (preferably) Fridays (total of 35 fractions). The second fraction will be given at least 6 hours after the first. Cohort 1 patients will receive cisplatin at a dose of 100 mg/m^2 IVPB over 60 minutes on Days 1 and 22 of RT.

### **5.2.3 Step Two, Cohort 2**

Cohort 2 patients will receive accelerated IMRT for a total dose of 70 Gy. It will be given over 6 weeks in once daily fractions Monday through Friday, with one additional fraction given on (preferably) Fridays (total of 35 fractions). The second fraction will be given at least 6 hours after the first. Cohort 2 patients will receive 7 weekly doses of cetuximab starting one week before RT and then weekly during RT. The cetuximab loading dose is 400 mg/m^2 IVPB and the remaining 6 weekly doses are 250 mg/m^2 IVPB. There is a +/- 2-day window for cetuximab dosing.

## **5.3 Study Procedures**

### **5.3.1 Baseline Assessment**

1. Office fiberoptic endoscopy (FOE) or operative room (OR) microlaryngoscopy (mDLx) to document the size and extent of the primary tumor site (PTS) along with research and routine biopsies of the PTS. Core or excisional biopsies of the involved neck nodes is an alternative approach to obtain tumor tissue.
2. p16INK4a IHC stain on all patients. HPV-HR (16,18) ISH will be required on all patients with p16INK4a positive oral cavity, larynx, and hypopharynx SCC.
3. Clinical examination with ECOG PS.
4. Weight.
5. Documentation of presence of PEG tube or tracheostomy tube
6. QOL assessment
7. CBC, CMP, Mg, PT/INR, PTT, pregnancy test (if woman of childbearing potential)
8. EKG
9. CT neck with IV contrast
10. FDG-PET/CT
11. Blood for genome sequencing

12. Primary disease site photographs

### **5.3.2 Step One Assessments**

1. Between Cycle 2 post-treatment Day 21 – Day 27, tumor response assessment will be performed by radiologic assessment with CT neck (with IV contrast).
2. Between Cycle 2 Days 18-22, office FOE or OR mDLx to document the size and extent of the PTS along with biopsy of the PTS. Core or excisional biopsies of the involved neck nodes is an alternative approach to obtain tumor tissue.
3. Between Cycle 2 Days 18-22 primary disease site photographs.
4. Clinical examination Cycle 1 Days 1, 15, and 22, and Cycle 2 Day 1 and 22.
5. CBC Days 1, 8, 15, and 22 of each cycle.
6. EKG Cycle 2: Day 1.
7. AE assessments weekly for two cycles.
8. Study Lab collection of 3 green top tubes for PBMC at C1D22 and C2D22.

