### **5.3.3 Step Two Cohort 1 Assessments**

Step Two will start the day after Cycle 2 Day 28 of neoadjuvant palbociclib monotherapy.

1. Clinical exam on Days 1, 8, 22, 29, and 36 then biweekly until adequate recovery from CRT toxicities per physician discretion.
2. CBC Days 1, 8, 22, and 29.
3. CMP, Mg Days 1 and 22. BMP, Mg on Days 8 and 29.
4. QOL assessment Days 1 and 36.
5. EKG Day 1.
6. AE assessments on Days 1, 8, 22, 29, and 36 during CRT.
7. Office FOE between 8-10 weeks after completion of CRT.
8. CT neck with IV contrast between 8-10 weeks after completion of CRT.
9. Primary disease site photographs between 8-10 weeks after completion of CRT.
10. FDG-PET/CT between 14-18 weeks after completion of CRT.

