### **5.3.5 Step Three Assessments**

Step Three will start 16 to 22 weeks after the completion of CRT.

1. Clinical examination Day 1 of each cycle.
2. CBC Day 1 of each cycle.
3. CMP, Mg Day 1 of each cycle.
4. EKG Day 1 of Cycles 1 and 4, and Day 29 of Cycle 6 (EOT).
5. QOL assessment at Cycle 1 Day 1, Cycle 4 Day 1, and Cycle 6 Day 29 (EOT).
6. AE assessments Day 1 of each cycle.
7. Study Lab collection of 3 green top tubes for PBMC at C1D22.
8. Thirty to 45 days after final cycle of adjuvant palbociclib, there will be a clinical examination, CBC, CMP, EKG, and AE assessment.

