## **6.0 DOSE DELAYS/DOSE MODIFICATIONS**

### **6.1 Dose Modifications for Palbociclib (Steps One and Three)**

Patients will be monitored for toxicity and the dose of palbociclib may be adjusted as indicated in the table below. Dose reduction by 1, and if possible, 2 dose levels will be allowed depending on the type and severity of toxicity encountered. Patients requiring more than 2 dose reductions will be discontinued from the study.

Recommended dose reductions for palbociclib are to decrease the current dose by 25 mg. The lowest dose available is 75 mg. Doses may be held as needed for toxicity resolution during a cycle. Doses omitted for toxicity are not replaced or restored within the same cycle (meaning that the cycle remains 28 days regardless of the number of doses of taken).

If a patient experiences toxicity which has not resolved to grade 2 or lower within two weeks (inclusive of the scheduled off-week), treatment with palbociclib should be permanently discontinued.

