### **Palbociclib Dose Modifications Based on Worst Treatment-Related Toxicity in the Previous Cycle**

Worst Toxicity During Previous Cycle	New Dose Level
Grade 4 neutropenia	- Withhold Palbociclib until recover to Grade $\leq$ 2. Resume at the next lower dose.
Grade 4 thrombocytopenia	- Withhold Palbociclib until recover to Grade $\leq$ 2. Resume at the next lower dose.
Grade 3 neutropenia associated with a documented infection or fever $\geq$ 38.5 °C	Withhold Palbociclib until recover to Grade $\leq$ 2. Resume at the next lower dose.
Grade $\geq$ 3 non-hematologic toxicity (includes nausea, vomiting, diarrhea, and hypertension only if persisting despite maximal medical treatment)	Withhold Palbociclib until symptoms resolve to 
 
• Grade <math>\leq</math> 1:
 
• Grade <math>\leq</math> 2 (if not considered a safety risk for the patient)
 
 Resume at the next lower dose.
Delay by > 1 week in receiving the next scheduled dose due to persisting treatment-related toxicities	If recovery to Grade $\leq$ 2 occurs within 2 weeks, continue and decrease by one dose level
Inability to deliver at least 80% of the planned dose of palbociclib due to adverse events possibly related to study treatment	Withhold Palbociclib until recovery to Grade $\leq$ 2. Decrease by one dose level.

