## **7.0 REGULATORY AND REPORTING REQUIREMENTS**

The entities providing oversight of safety and compliance with the protocol require reporting as outlined below. Please refer to Appendix F for definitions and Appendix G for a grid of reporting timelines.

Adverse events will be tracked from the start of treatment through 30 days following the last day of study treatment. All adverse events must be recorded on the toxicity tracking case report form (CRF).

Refer to the data submission schedule in Section 12 for instructions on the collection of AEs in the EDC.

Reporting requirements for Washington University study team may be found in Section 7.1.

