### **7.1.3 Reporting to Pfizer**

Within 24 hours of first awareness of the event (immediately if the event is fatal or life-threatening), the PI or designee will report to Pfizer by facsimile any serious adverse drug experience (as defined in Appendix F) that occurs during the SAE reporting period (as defined in Section 7.0) in a study subject receiving palbociclib. Such SAEs will be reported using MedWatch form and the Pfizer Reportable Event Fax Cover Sheet (Appendix C) should also be included. SAEs should be reported as soon as they are determined to meet the definition, even if complete information is not yet available.

Even though there may not be an associated SAE, exposure to palbociclib during pregnancy or lactation is reportable. In addition, occupational exposure to palbociclib is reportable, and a lack of effect of palbociclib may also be reportable.

Hy's Law Cases: Cases of potential drug-induced liver injury as assessed by laboratory test values ("Hy's Law Cases") are also reportable to Pfizer. If a study subject develops abnormal values in aspartate transaminase (AST) or alanine transaminase (ALT) or both, concurrent with abnormal elevations in total bilirubin and no other known cause of liver injury, that event would be classified as a Hy's Law Case.

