#### **8.1.7 Administration**

Patients should be encouraged to take their dose of PD 0332991 at approximately the same time each day. Patients should be instructed to record daily administration of the study drugs in a patient diary.

Patients must be instructed to withhold their daily dose of PD 0332991 on

pharmacokinetic sampling days until the pre-dose pharmacokinetic sample and safety assessments (ie, hematology, blood chemistry and ECGs) have been completed. On days the patient is in the clinic, PD 0332991 will be taken when instructed by the investigator.

Patients who miss a day's dose must be instructed NOT to "make it up" the next day. Patients who vomit any time after taking a dose must be instructed NOT to "make it up," and to resume treatment the next day as prescribed. Patients who inadvertently take 1 extra dose during a day must be instructed to skip the next day's dose

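### Step One schedules no chemistry or magnesium across 42 palbociclib dosing days, so asymptomatic hepatic, renal or electrolyte toxicity cannot inform the Cycle 2 dose

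*Combined protocol and SAP*

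**What the plan says.** Step One gives palbociclib 125 mg/day on Days 1-21 of two 28-day cycles (Section 5.2.1). Section 5.3.2 schedules "CBC Days 1, 8, 15, and 22 of each cycle", one EKG at Cycle 2 Day 1, clinical examinations, weekly adverse event assessments and research blood. It lists no CMP, BMP or magnesium. The CMP and magnesium row of calendar 10.1 has a single mark, under baseline, and baseline tests may be up to 28 days before enrollment.

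The next chemistry is at Step Two: Day 1 for Cohort 1 (Section 5.3.3) and the day of the cetuximab loading dose for Cohort 2 (Section 5.3.4). On timing, the plan says "Step Two will start the day after Cycle 2 Day 28 of neoadjuvant palbociclib monotherapy".

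Section 6.1 applies to Steps One and Three. Its table is headed "Palbociclib Dose Modifications Based on Worst Treatment-Related Toxicity in the Previous Cycle" and includes Grade 3 or higher non-hematologic toxicity. A further rule stops palbociclib permanently; its condition begins "If a patient experiences toxicity which has not resolved to grade 2 or lower within two weeks (inclusive of the scheduled off-week".

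Step Three gives the same drug, dose and cycle length and has "CMP, Mg Day 1 of each cycle" (Section 5.3.5).

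Section 3.1.2 allows Cohort 2 patients to enter with creatinine clearance of 30-75 mL/min, bilirubin of 1.5-2 x IULN, or ALT and AST of 2.5-5 x IULN.

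**The concern.** Dose rules work only if the toxicity they act on is measured in time. For severe liver, kidney or electrolyte toxicity without symptoms, Step One schedules no test that could trigger the Section 6.1 rules before Cycle 2 dosing has finished. An abnormality that arises and resolves within Step One would not be recorded from scheduled tests at all. One that persists would first be seen on the day chemoradiation, or the cetuximab lead-in to it, is due to begin.

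Hy's Law cases are reportable and are defined by laboratory values: "If a study subject develops abnormal values in aspartate transaminase (AST) or alanine transaminase (ALT) or both, concurrent with abnormal elevations in total bilirubin" (Section 7.1.3). Those values are not scheduled while Step One palbociclib is being taken.

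The patients most exposed are those in Cohort 2 who already have impaired renal or hepatic function. They receive two cycles with no scheduled recheck of the function that placed them in that cohort.

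**Working it through.** The plan states no figure to reproduce. The check is a count of scheduled tests and days, with study Day 1 = Cycle 1 Day 1.

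**Inputs.** Dosing days and cycle length: Section 5.2.1. Step One tests: Section 5.3.2 and calendar 10.1. Step Two start and first panels: Sections 5.3.3 and 5.3.4. Baseline window: calendar 10.1, note 4. Sample size of 24: Section 14.4.

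**Current schedule**
- Planned dosing days: 2 x 21 = 42, over 2 x 28 = 56 days.
- CBC draws: 2 x 4 = 8. Chemistry or magnesium draws: 0.
- Cycle 2 Day 1: 28 + 1 = Day 29. Last planned dose (Cycle 2 Day 21): 28 + 21 = Day 49. Step Two start: 56 + 1 = Day 57.
- Last dose to next panel: 57 - 49 = 8 days.
- Longest time without a panel: 57 - 1 = 56 days if baseline chemistry is drawn on Day 1. If it is drawn 28 days before enrollment and dosing starts at enrollment (an assumption), the interval is 56 + 28 = 84 days.

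**Which Section 6.1 rules lack a scheduled input**

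| Rule | Scheduled input in Step One |
|---|---|
| Grade 4 neutropenia | CBC |
| Grade 4 thrombocytopenia | CBC |
| Grade 3 neutropenia with infection or fever | CBC, exams, AE assessments |
| Grade 3 or higher non-hematologic | Exams and AE assessments if symptomatic; none for asymptomatic chemistry |
| Delay of more than 1 week | CBC and symptoms; none for asymptomatic chemistry |
| Less than 80% of planned dose delivered | CBC and symptoms; none for asymptomatic chemistry |
| Two-week discontinuation rule | CBC and symptoms; none for asymptomatic chemistry |
| QTc (6.1.1) | EKG at Cycle 2 Day 1 |

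The missing input is thus the asymptomatic chemistry component of four rules. There is one between-cycle dose decision in Step One (Cycle 2, Day 29), and it is taken without scheduled chemistry.

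**Schedule after a change**

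| Panels added | Intervals from Day 1 to Day 57 (days) | Longest | Longest if baseline was 28 days early |
|---|---|---|---|
| None | 56 | 56 | 84 |
| C2D1 (Day 29) | 28, 28 | 28 | 28 + 28 = 56 |
| C1D15 and C2D1 | 14, 14, 28 | 28 | 28 + 14 = 42 |
| C1D15, C2D1 and C2D22 (Day 50) | 14, 14, 21, 7 | 21 | 28 + 14 = 42 |

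Cycle 2 Day 1 alone halves the minimum gap and is the only addition that falls on the day of the Cycle 2 dose decision.

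**The case against.** The best defence is that the schedule follows the stated risk. Section 1.4 gives neutropenia as the dose-limiting toxicity, and Step One monitors it with 8 blood counts. Section 8.1.9 counts the nonclinical liver-enzyme and renal findings as non-adverse at tolerated doses, with partial or full reversibility. The text available for this review attributes hypomagnesemia to cetuximab (Section 6.3.7), not to palbociclib. Text and calendar agree, so this is a choice rather than a drafting slip. Symptomatic toxicity reaches the Section 6.1 rules through weekly adverse event assessments, and nothing forbids unscheduled chemistry. Cisplatin dosing is protected by the Step Two Day 1 panel. All of this stands, and it keeps the point small. It does not supply a chemistry result before the Cycle 2 dose, and discretionary ordering gives no assurance that every patient has one.

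Several stronger readings are tempting but not supported:

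- *All asymptomatic laboratory toxicity goes unseen until Step Two.* It does not: the blood counts detect neutropenia and thrombocytopenia during both cycles.
- *The Section 6.1 dose table and the two-week rule have no laboratory input.* Three of the six table rows are driven by blood counts, and blood counts also feed the two-week rule.
- *QTc is unmonitored.* The Cycle 2 Day 1 EKG checks it directly. What is missing is only a set of electrolytes beside it, which would help where Section 6.1.1 asks whether a reversible cause was found.
- *Step Three shows that Step One needs the same panels.* Step Three patients have had cisplatin or cetuximab with radiation and then take six cycles. It is a scheduling precedent only.
- *A Hy's Law case would escape reporting.* A persisting case would be found at Step Two, within the tracking period: "Adverse events will be tracked from the start of treatment through 30 days following the last day of study treatment" (Section 7.0). It would be found late.
- *A given number of patients would be affected.* I found no rate of asymptomatic severe chemistry toxicity in the text available, so any such number would only restate an assumed rate.

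One passage might seem to close the gap. Section 8.1.7 tells patients to hold the dose on "pharmacokinetic sampling days until the pre-dose pharmacokinetic sample and safety assessments (ie, hematology, blood chemistry and ECGs) have been completed". Step One schedules no pharmacokinetic sampling days, so this creates no chemistry draw.

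**Conclusion.** The point holds in its narrow form. Between baseline and Step Two start, 42 planned dosing days pass with no scheduled chemistry or magnesium. Asymptomatic hepatic, renal or electrolyte toxicity therefore cannot be detected from scheduled tests in time to inform the Cycle 2 dose. The interval without a panel is at least 56 days, and 84 days under the early-baseline assumption.

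The Day 57 figure assumes that Step Two starts as planned; a delayed start would push the first panel later unless chemistry is ordered in the meantime. The frequency of the toxicity is not established, and neither is the number of Cohort 2 patients who would enter with impaired organ function, since some qualify on ECOG performance status alone. The schedule count is certain; the size of the clinical harm is not. The primary response analysis is unaffected. I would class this as a cheap improvement to consider.

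**What to change.** Add CMP and magnesium at Cycle 2 Day 1, in both Section 5.3.2 and calendar 10.1, with the result reviewed before the Cycle 2 dose is set. A CBC draw, an examination and the EKG already take place that day, so no visit or procedure is added.

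Two further panels are optional, also at existing CBC draws:
- **Cycle 1 Day 15:** an on-drug value, 29 - 15 = 14 days before Cycle 2 Day 1, so a severe result can be read against the two-week rule.
- **Cycle 2 Day 22:** 57 - 50 = 7 days of notice before cisplatin or cetuximab. This is lead time only, since the cisplatin dose is already guarded by the Step Two Day 1 panel and Section 6.2.3.

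Cost: 24 x 1 = 24 routine panels for Cycle 2 Day 1 alone, 24 x 2 = 48 with Cycle 1 Day 15, and 24 x 3 = 72 with all three, plus the calendar amendment.
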